6.3 Baseline Assessments

The baseline measurement is the last predose measurement taken before first study treatment dose.

The following baseline assessments will be conducted prior to initial study drug administration:

- Age
- Race
- Height
- Weight
- Menopausal Status
- **Medical History**
- Physical examination
- **ECOG Performance Status**
- Laboratory tests
- Pregnancy test
- 12-lead ECGs
- Radiological assessment

6.4 Efficacy Variables

All efficacy parameters will be summarized using ITT and PP analysis set.

6.4.1 Primary Efficacy Variable

The primary efficacy variable is the percentage of patients without disease progression at the end of 6 months i.e. 180 days:

Percentage = (patients without disease progression/total number of patients) *100.

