5 TREATMENT OF PATIENTS

5.1 Administration of Tenalisib

Tenalisib will be administered orally twice daily in a 28-day cycle (Day 1-28) up to 2 years until progression of disease or toxicity warranting discontinuation of therapy.

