6.9 End of Study (EOS) Visit

All patients must be followed up telephonically for adverse events for 30 calendar days after the last dose of study drug. In case of drug related SAE/AE or treatment discontinuation due to adverse event, the patients will be followed till the resolution/stabilization of the AE or 30 days after the last study dose whichever is the earlier.

CONFIDENTIAL Page 37 of 66

| Table 5 : Schedule of Events | | | | | | | | | | |
|---|-----------|----|-----|----|-----|----|---|---|-------------------|-------------------|
| Cycle | Screening | (| C1 | Ó | 22 | С3 | Monthly visits (C4 onward up to 2 year) ¹⁹ | Efficacy Visits (C5, C7, C9 up to 2 year) ²⁰ | EOT ²¹ | EOS ²² |
| Day | D-28 to 0 | D1 | D15 | D1 | D15 | D1 | D1 | D1 | - | - |
| Window period | - | | ±1 | ±1 | ±3 | ±3 | ±3 | ±7 | +7 | +30 |
| Study Days | D-28 to 0 | 1 | 15 | 29 | 43 | 57 | - | - | - | - |
| Informed Consent ¹ | X | - | - | - | - | - | - | - | - | - |
| Demographics ² | X | - | - | - | - | - | - | - | - | - |
| Medical history ³ | X | X | - | - | - | - | - | - | - | - |
| Vitals ⁴ | X | X | X | X | X | X | X | - | X | - |
| Height and weight ⁵ | X | X | X | X | X | X | X | - | X | - |
| Physical examination ⁶ | X | X | X | X | X | X | X | - | X | - |
| ECOG Performance Status | X | X | - | X | - | - | X | - | X | - |
| Complete blood count ⁷ | X | X | X | X | X | X | X | - | X | - |
| Chemistry panel I ⁸ | X | X | X | X | X | X | X | - | X | - |
| Chemistry panel II ⁹ | X | X | - | X | - | X | X | - | X | - |
| HIV, HBV, HCV status | X | - | - | - | - | - | - | - | - | - |
| PT and INR ¹⁰ | X | X | = | X | - | X | - | - | X | = |
| Cytokines/chemokines analysis ¹¹ | X | - | - | - | - | X | - | - | - | - |
| Urinalysis (routine) | X | X | X | X | X | X | X | - | X | - |
| Pregnancy test ¹² | X | X | - | - | - | - | - | - | - | - |
| 12-lead ECGs ¹³ | X | X | - | X | - | X | - | - | X | - |
| Tumour biopsy 14 | X | - | - | - | - | X | - | - | - | - |
| Radiological assessment (CT and/or MRI) 15 | X | - | - | - | - | X | - | X | X | - |
| Bone scan ¹⁶ | X | - | - | - | - | - | - | - | - | - |
| Drug Dispensing ¹⁷ | - | X | - | X | - | X | X | - | - | - |

CONFIDENTIAL Page 38 of 66

Version 1.0, Dated June 29, 2021

| Tenalisib administration ¹⁸ | - | X | X | X | X | X | X | - | - | - |
|--|---|---|---|---|---|---|---|---|---|---|
| Drug compliance | - | X | X | X | X | X | X | - | X | - |
| AE evaluation | X | X | X | X | X | X | X | - | X | X |

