- 19. All visits will be done monthly from Cycle 3 onwards for 24 months (e.g. C4, C5, C6.... C26).
- 20. All visits for efficacy assessments will be done at 8-weekly intervals (± 7 days) for 24 months (e.g.C5, C7.... C26).
- 21. All patients will undergo the end-of-treatment (EOT) assessments within 7 days after last dose of study drug or discontinuation.
- 22. Patients must be followed telephonically for adverse events for 30 calendar days after the last dose of study drug.

CONFIDENTIAL Page 40 of 66

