7.6 Dose Modifications

In case of hematologic and non-hematologic toxicities, the dose modifications provided below (**Table 6** and **Table 7**) should be used as a guidance and should be determined as per PI's clinical judgement. The dose modifications are intended to be applied when the investigator determines the events related to tenalisib. If events (cytopenia) are deemed related to the underlying disease rather than tenalisib, dose reduction will be done as per the investigator's discretion. In case of drug withhold, tenalisib treatment can be resumed if:

- Patient recovers from grade 3-4 toxicity as defined in dose modification guidance below.
- No clinical or radiographic evidence of disease progression.
- Investigator believes the risk of progression outweighs the risk of further treatment.

If treatment is delayed >2 weeks, treatment continuation should be discussed with Medical monitor. The treatment should be permanently discontinued if withhold of study drug due to drug related toxicity is for > 28-days unless approved by medical monitor.

At the discretion of the investigator, a dose re-escalation may be permitted for patients who earlier has dose reduction. The decision should be taken after evaluating the emerging safety data and benefit and risk of re-escalation. Drug holidays are discouraged. Any patient in whom similar toxicity recurs at the reduced dose, it should be discussed with medical monitor to determine appropriate strategy on treatment continuation.

CONFIDENTIAL Page 46 of 66

Table 6: Dose modifications for hematologic toxicity

| CTCAE Grade | Action to be Taken |
|--|---|
| Hematologic toxicity | |
| Grade 3 Neutropenia $(1.0 \times 10^9/L < ANC \ge 0.5 \times 10^9/L)$ | Maintain dose level.Monitor ANC at least weekly. |

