8 ASSESSMENT OF EFFICACY

8.1 Specification of the Efficacy Parameters

Initial disease assessment of patients should be performed within 28 days prior to the first dose of study drug using computed tomography (CT) and/or magnetic resonance imaging (MRI). This scan will be considered as baseline scan. The PI should review baseline scan images to confirm the subject has measurable disease as defined in the inclusion criteria. Scan performed as part of routine clinical management is acceptable for use as the baseline scan if it is of diagnostic quality and performed within 28 days prior to the C1D1, or as approved by the medical monitor if it is out of window period.

Subsequent scan (CT and/or MRI as applicable) should be done at C3D1 (± 7 days) and approximately 8 weeks thereafter (± 7 days), and/ or at the EOT and so on or as clinically indicated (if clinical progression is suspected). If a CR or PR is noted, confirmatory scans should be performed at least 4 weeks after the initial response was first documented. The scan should be reviewed by site investigator/radiologist/designee and tumour response will be assessed according to the revised Response Evaluation Criteria in Solid Tumour guideline (RECIST) version 1.1.[21]

8.2 Images included in the assessment.

A CT with IV contrast will be the primary modality for assessment, unless the patient has an allergy to contrast that cannot be controlled with pre-medications. If patients are unable to receive iodinated CT contrast, the preferred imaging is non-contrast CT of the chest, and MRI of the abdomen and pelvis with contrast. Tumour imaging should remain consistent throughout study and should include those thought by investigator to best capture status of disease. For skin nodules, CT or MRI will be the preferred modality of assessment. Digital photography will not be acceptable as a method of assessment for skin lesions.

8.3 Measurable and non-measurable disease:

Eligibility of lesions for quantitative assessment will be determined at baseline, with target lesions selected from the measurable lesions identified. After baseline, target lesions will always be assessed quantitatively, and non-target lesions will be assessed qualitatively, with no further evaluation of measurability according to these definitions.

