6.2 Time Point Algorithms

6.2.1 Relative Day

The date of first dose of study drug will be considered relative day 1, and the day before the first dose of study drug will be relative day -1. Relative days will be calculated as follows only when the full assessment date is known (i.e., partial dates will have missing relative days):

For days on or after the first dose of study drug:

Date of Assessment – Date of First Dose of Study Drug + 1.

For days before the first dose of study drug: Date of Assessment – Date of First Dose of Study Drug.

CONFIDENTIAL Page 8 of 106
Document Date: 12MAY2023. ST-AD-032 version 01

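### The 180-day primary cut, applied through treatment duration, does not match the C7D1 scan (day 169 ±7), and no rule covers a late or missed scan

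*SAP*

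**What the plan says.** **Time point.** SAP 6.4.1 defines the primary variable as the "percentage of patients without disease progression at the end of 6 months i.e. 180 days", with no tolerance and no named scan. The footnote to the Table 14.2.1.1 shell says that the 6-month row summarises patients treated for 180 days or more, with percentages taken over all patients in the group. SAP 8.8.1 computes treatment duration as last dosing day minus first dosing day plus 1.

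**Scan schedule.** Protocol Table 5 lists "Efficacy Visits (C5, C7, C9 up to 2 year" after the C3D1 scan. Its footnote 20 says "All visits for efficacy assessments will be done at 8-weekly intervals (± 7 days) for 24 months". Protocol 8.1 is looser: scans "should be done at C3D1 (± 7 days) and approximately 8 weeks thereafter (± 7 days"). Scans are also allowed at end of treatment and whenever progression is suspected. The end-of-treatment scan is not needed if one was done in the previous 28 days.

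**Late or missed scans.** SAP 6.2.2 recalculates visits in study days from first drug, but from C4 onward it gives no study day, only ±3 or ±7. SAP 7.3 imputes no missing results. No text says which scan decides 6-month status.

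**The neighbouring rule.** For clinical benefit (CBR), the Table 14.2.2.1 footnote counts stable disease of 24 weeks or more from a treatment duration of 168 (±7) days.

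**The concern.** Progression is dated when it is imaged. A cut at day 180, between two scan windows, means that status on that day is carried forward from an earlier scan. The footnote adds a second condition, time on drug, which is not tumour status. Two patients with the same disease course can then be classified differently because of a scan date or a last-dose date.

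What is at stake is the primary proportion in each arm. Protocol 1.5.2 says the trial is meant to identify the better of two doses. With 20 patients per arm, one reclassified patient is visible in the result.

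**Working it through.** **1. Inputs.** SAP 6.2.1: "The date of first dose of study drug will be considered relative day 1". Protocol 5.1: "Tenalisib will be administered orally twice daily in a 28-day cycle (Day 1-28"). Scan window ±7 days (Protocol Table 5). Cut: day 180 (SAP 6.4.1). Patients per arm: 20.

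**2. Reproduce the plan's own days.** Day d of cycle k falls on study day 28(k − 1) + d. For C1D1, C1D15, C2D1, C2D15 and C3D1 this gives 1, 15, 29, 43 and 57. Protocol Table 5 prints the same: "Study Days | D-28 to 0 | 1 | 15 | 29 | 43 | 57".

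**3. Extend to later scans, anchored to first dose.**
- C5D1 = 28 × 4 + 1 = 113 (106 to 120)
- C7D1 = 28 × 6 + 1 = 169 (162 to 176)
- C9D1 = 28 × 8 + 1 = 225 (218 to 232)

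No routine window covers days 177 to 217. The C7 window closes 180 − 176 = 4 days before the cut.

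**4. The other reading: 8 weeks ±7 days after the previous scan.** Each step adds 49 to 63 days.
- Scan 1: 50 to 64
- Scan 2: 99 to 127
- Scan 3: 148 to 190
- Scan 4: 197 to 253

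Here a third scan on days 181 to 190 complies with the protocol and falls after the cut.

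**5. Run patients through the rules as written.**
- Progression on a C7 scan on day 176: dated before the cut, a failure. Delay inside the window cannot change the result.
- C5 clean, C7 done on day 183, progression first seen then, drug taken until then: no progression dated by day 180 and treatment over 180 days, so a success. On the anchored reading this scan is 183 − 176 = 7 days out of window; on the rolling reading it can be compliant.
- C7 missed, progression first seen at C9 on day 225, still on drug: also a success.
- Stable disease at C7 on day 169, drug stopped for toxicity on day 175, no progression: not a success under the footnote, since 175 < 180, though still in the denominator. Under the CBR rule the patient qualifies, since 175 meets even 168 + 7.

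**6. Size per patient.** 1/20 = 5 percentage points. For example, 4/20 = 20% (exact 95% CI 5.7 to 43.7) becomes 5/20 = 25% (8.7 to 49.1).

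**7. Scale, under an assumption.** Take a constant hazard calibrated to the planned 20% at day 180: S(t) = 0.2^(t/180).
- On-time patients: S(162) = 23.5%, S(169) = 22.1%, S(176) = 20.7%. The excess over 20% is 3.5, 2.1 or 0.7 points, which is 0.7 to 0.15 patients per arm of 20.
- Patients whose progression would first show at C7: S(113) − S(169) = 36.4% − 22.1% = 14.3%, and 0.143 × 20 = 2.9 patients per arm. These are open to a switch if their C7 scan is late or missed. How many scans will be is not given.

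**The case against.** The strongest reply is that C7 is in practice the 6-month scan, done within 4 to 18 days of the cut. For on-time patients the mismatch is worth less than one patient per arm. That stands.

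Three stronger readings are tempting, and the documents do not support them.

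- **That disease status at 6 months is never measured.** End-of-treatment and clinically indicated scans can fall on any day, and the rolling reading puts day 180 inside the third window. What is missing is a routine window around day 180 on the anchored schedule.
- **That any delay of the C7 scan turns a progressor into a success.** Only a scan on day 181 or later does so.
- **That dose holds delay the scan and so favour the higher dose.** Protocol 7.6 does allow long holds: permanent discontinuation applies if "withhold of study drug due to drug related toxicity is for > 28-days unless approved by medical monitor". If visits moved with a hold, 181 − 169 = 12 days would be enough. But no text says that they move. Table 5 footnote 20 reads as calendar spacing, SAP 6.2.2 counts from first drug, and the documents give no hold rates by dose.

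It can also be said that a scan outside its window is a protocol deviation, that the medical monitor reviews deviations for per-protocol exclusion, and that the primary endpoint is repeated in that set. This helps only in part. ITT is the primary population, and exclusion removes the patient rather than classifying the outcome correctly. On the rolling reading there may be no deviation at all.

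**Conclusion.** The point holds as a mismatch between the primary cut, its table footnote and the scan schedule, with no rule for a late or missed C7 scan. It can act in either direction: a late or missed scan can create a success, and an early stop after a clean C7 scan can remove one.

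Each affected patient is worth 5 points in an arm of 20. The number affected, and whether it differs between 800 and 1200 mg BID, cannot be known from the documents, so no directional bias between doses should be claimed. The dates follow from the documents alone. The scale figures (0.15 to 0.7 patients for on-time scans, 2.9 patients open to a switch) rest on the constant-hazard assumption, and the second also assumes that no such progression is caught by a clinically indicated scan.

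Severity: should-fix. The trial estimates one proportion per arm with wide intervals and plans no between-arm efficacy test, but the correction is cheap.

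**What to change.** **SAP 6.4.1 and Table 14.2.1.1.** Define the primary endpoint as alive without RECIST progression through the week-24 assessment (C7D1, day 169 ±7). SAP 6.4.1 does not mention death, so this should be explicit. Replace the treatment-duration footnote, including in the tables that reuse the format. Point the primary endpoint and the CBR rule to the same C7D1 assessment.

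**Late or missed C7 scan.** Use the next scan and count progression found there as progression. Count patients with no later scan as not progression-free, and report how many there are, because SAP 5.1 says the study closed before all patients had progressed.

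**Sensitivity analysis.** The next-scan rule is conservative: progression that began after week 24 can count against the patient. Add a Kaplan-Meier estimate for week 24 from the PFS analysis already planned. Read it at day 176, the close of the C7 window, because a reading at day 168 would miss progression dated on the nominal scan day, 169.

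**SAP 6.2.2.** State whether scan dates are counted from first dose or move with dose interruptions. Protocol footnote edits would add little now that the study has closed.

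**Cost.** Wording, table footnotes and one extra reading from an existing analysis; no new scans. The endpoint is labelled 24 weeks, some late-scanned patients move to failure, and the change must be recorded in SAP 5.2, which now reports none. It should be made before database lock.

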3 TRIAL DESIGN

3.1 Trial End Points

3.1.1 Primary Endpoint

- Percentage of patients without disease progression at the end of 6 months.

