7.4.4 Deaths

Deaths that occur during the protocol-specified AE reporting period that are attributed by the investigator solely to progression of disease will be recorded on the "Trial Discontinuation" eCRF and should not be reported as a SAE. All other on- trial deaths, regardless of attribution, will be recorded on an SAE Report and expeditiously reported to the Sponsor.

When recording a serious adverse event with an outcome of death, the event or condition that caused or contributed to the fatal outcome should be recorded as the single medical concept on the SAE report and Adverse Event page of the eCRF. If the cause of death is unknown and cannot be ascertained at the time of reporting, record "Death NOS" on the eCRF Adverse Event page.

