6.4.3 Additional Efficacy Variables

Duration of Treatment Exposure: Duration of treatment exposure is defined as the time from first dose to last dose of drug.

Duration of Response: Duration of response (DoR) is defined as the time from the first occurrence of partial or complete response to disease progression or death in patients who achieve complete or partial response. For patients who neither progress nor die, the duration of response will be censored on the last date the patient is known to be radiologically progression free.

Duration of clinical benefit: Duration of clinical benefit (DoCB) is defined as the time from the first dose of study drug to disease progression or death in patients who achieve complete response, partial response, or stable disease for 24 weeks or longer. For patients who neither progress nor die, the duration of response will be censored on the last date the patient is known to be radiologically progression free.

Proportion of patients with 6-Month and 1-year PFS.

PFS rate at 6-months or at 1-year: Proportion of patients who remained alive and progression-free at 6 months or at 1-Year

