A patient with two or more prior non-drug treatments in the same system organ class (or with the same preferred term) is counted only once for that system organ class (or preferred term).

System organ classes are sorted in alphabetical order. Preferred terms are sorted within system organ class by descending order of frequency of overall preferred terms.

Prior non-drug treatments are those that were taken only prior to the first dose of study drug.

Reference Listing 16.2.x.x

Document Date: 12MAY2023.

Protocol RP6530-2101 Table 14.1.5.4 Summary of Concomitant Non-Drug Treatments Safety Analysis Set Page xx of yy

System Organ Class	Tenalisib 800 mg BID	Tenalisib 1200 mg BID	Overall
Preferred Term	(N=XX)	(N=XX)	(N=XX)
	n (%)	n (%)	n (%)
Patients with at least one Concomitant	xx (xx.x)	xx (xx.x)	xx (xx.x)
Non-Drug Treatment			
SOC1	xx (xx.x)	xx (xx.x)	xx (xx.x)
PT1	xx (xx.x)	xx (xx.x)	xx (xx.x)
PT2	xx (xx.x)	xx (xx.x)	xx (xx.x)
Etc.			

Percentages are based on the total number of patients (N) in each treatment group.

A patient with two or more concomitant non-drug treatments in the same system organ class (or with the same preferred term) is counted only once for that system organ class (or preferred term).

Non-drug treatments are coded using MedDRA (version 24.0).

System organ classes are sorted in alphabetical order. Preferred terms are sorted within system organ class by descending order of frequency of overall preferred terms.

Concomitant non-drug treatments are those that were taken while on study drug. The non-drug treatments that started after the discontinuation of study drug will also be termed as 'Concomitant non-drug treatments'

Reference Listing 16.2.x.x

Document Date: 12MAY2023.

Protocol RP6530-2101

Table 14.2.1.1

Summary of Patients Without Disease Progression at the End of 6 Months

ITT Analysis Set

	Tenalisib 800 mg BID	Tenalisib 1200 mg BID	Overall
	(N=xx)	(N=xx)	(N=xx)
Number (%) of patients without progression at the End of 6 months 95% CI*	xx (xx.x)	xx (xx.x)	xx (xx.x)
	(xx.x, xx.x)	(xx.x, xx.x)	(xx.x, xx.x)

The Intent - to - Treat (ITT) analysis set includes all patients who received at least 1 dose of study medication.

Percentages are based on the total number of patients (N) in each treatment group.

At 6 months, patients with treatment duration ≥180 days are summarized.

Reference Listing 16.2.x.x

Document Date: 12MAY2023

Program: xx.sas Table Generation: ddmmmyyyy hh:mm:ss

Use same format for

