- 1. Table 14.2.1.2 Summary of Patients without Disease Progression at the End of 6 Months by Type of Metastasis ITT Analysis Set <Column 1: same as table 14.2.1.1; Column 2: de novo metastasis; Column 3: recurrent metastasis; Column 4: Overall>
- 2. Table 14.2.1.3 Summary of Patients without Disease Progression at the End of 6 Months Per Protocol Analysis
- 3. Table 14.2.1.4 Summary of Patients with 6-Month and 1-Year Progression Free Survival ITT Analysis Set
 - <Column 1: First line "Number (%) of patients without Progressive disease/Death at 6 Month" Second line "Number (%) of patients without Progressive disease/Death at 1 year;

Add footnote-"At 1 year, patients with treatment duration ≥360 days are summarized."

- 4. Table 14.2.1.5 Summary of Patients with 6-Month and 1-Year Progression Free Survival by Type of Metastasis ITT Analysis Set
 - <Column 1: First line "Number (%) of patients without Progressive disease/Death at 6 Month"

 Second line "Number (%) of patients without Progressive disease/Death at 1 year;

Add footnote-"At 1 year, patients with treatment duration ≥360 days are summarized."

Column 2: de novo metastasis; Column 3: recurrent metastasis; Column 4: Overall>

5. Table 14.2.1.6 Summary of Patients with 6-Month and 1-Year Progression Free Survival – Per Protocol Analysis

^{*} The 95% CIs are reported using exact method based on binomial distribution.

Protocol RP6530-2101

Table 14.2.2.1

Summary of Objective Response Rate and Clinical Benefit Rate

ITT Analysis Set

	Tenalisib 800 mg BID	Tenalisib 1200 mg BID	Overall
	(N=xx)	(N=xx)	(N=xx)
Number (%) of patients			
95% CI*			
CR	xx (xx.x)	xx (xx.x)	xx (xx.x)
	(xx.x, xx.x)	(xx.x, xx.x)	(xx.x, xx.x)
PR	xx (xx.x)	xx (xx.x)	xx (xx.x)
	(xx.x, xx.x)	(xx.x, xx.x)	(xx.x, xx.x)
SD	xx (xx.x)	xx (xx.x)	xx (xx.x)
	(xx.x, xx.x)	(xx.x, xx.x)	(xx.x, xx.x)
SD>=24 weeks	xx (xx.x)	xx (xx.x)	xx (xx.x)
	(xx.x, xx.x)	(xx.x, xx.x)	(xx.x, xx.x)
PD	xx (xx.x)	xx (xx.x)	xx (xx.x)
	(xx.x, xx.x)	(xx.x, xx.x)	(xx.x, xx.x)
Not Evaluated	xx (xx.x)	xx (xx.x)	xx (xx.x)
	(xx.x, xx.x)	(xx.x, xx.x)	(xx.x, xx.x)
ORR (CR+PR)	xx (xx.x)	xx (xx.x)	xx (xx.x)
	(xx.x, xx.x)	(xx.x, xx.x)	(xx.x, xx.x)
CBR (CR+PR+SD>=24 weeks)	xx (xx.x)	xx (xx.x)	xx (xx.x)
,	(xx.x, xx.x)	(xx.x, xx.x)	(xx.x, xx.x)

The ITT analysis set includes all patients who received at least 1 dose of study medication. Percentages are based on the total number of patients (N) in each treatment group.

CONFIDENTIAL

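### The primary 6-month percentage has two conflicting rules: under SAP 6.4.1 a death before day 180 without documented progression is a success, while the Table 14.2.1.1 footnote fails it through treatment duration

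*SAP*

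**What the plan says.** Protocol 3.1.1 sets the primary endpoint as "Percentage of patients without disease progression at the end of 6 months". SAP 6.4.1 fixes the day ("The primary efficacy variable is the percentage of patients without disease progression at the end of 6 months i.e. 180 days") and gives the formula "Percentage = (patients without disease progression/total number of patients) *100". SAP 8.7.1 adds an exact binomial 95% interval but no further definition. None of the three mentions death.

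Elsewhere the SAP names death when it means to count it. PFS (6.4.2) and the durations of response and of clinical benefit (6.4.3) all take death as an event. SAP 6.4.3 also defines a separate 6-month PFS rate: "Proportion of patients who remained alive and progression-free at 6 months or at 1-Year". The shells in SAP section 12 keep the two apart. The primary row in Table 14.2.1.1 reads "Number (%) of patients without progression at the End of 6 months", and the row in Table 14.2.1.4 reads "Number (%) of patients without Progressive disease/Death at 6 Month".

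The footnote to Table 14.2.1.1 then brings in a criterion that 6.4.1 does not contain: "At 6 months, patients with treatment duration ≥180 days are summarized", with percentages over all N in the group. SAP 8.8.1 calculates treatment duration as last dosing day minus first dosing day plus 1.

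SAP 7.3 rules out imputing missing results or events. Under Protocol 7.4.4, deaths "attributed by the investigator solely to progression of disease will be recorded on the" Trial Discontinuation eCRF and are not reported as SAEs.

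(Table numbers here follow the shells. The SAP's list of outputs gives the number 14.2.1.3 to four different tables.)

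**The concern.** A 6-month endpoint that fails a patient only for progression leaves early deaths unclassified, and a literal reading of the formula puts them in the numerator. The contrast between the two row labels invites a programmer to read it that way.

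Such deaths are possible under this schedule. The first post-baseline scan is at C3D1, day 57, and the next two fall about day 113 (57 + 56) and day 169 (113 + 56). A patient who dies before the first scan may have no post-baseline assessment; the shells then give a best response of not evaluated, and nothing in SAP 7.3 turns that patient into a failure.

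At stake is the figure meant to show anti-tumour activity. Protocol 1.5.2 says the trial is to identify the better of the two doses, with 20 patients per arm. A rule that lets a death raise an arm's efficacy percentage works in the wrong direction for that choice. A rule that depends on time on drug mixes tolerability into an activity endpoint.

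**Working it through.** **Inputs.** n = 20 per group and an assumed 6-month rate of 20%, so 4/20 (Protocol 9.2, SAP 4.5). Exact binomial 95% interval (SAP 8.7.1). Day 180 (SAP 6.4.1). The number *d* of deaths before day 180 without documented progression is not given; I assume 0 to 3 per group.

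**The plan's own figure.** The Clopper-Pearson lower limit is the α/2 quantile of Beta(x, n − x + 1), and the upper limit is the 1 − α/2 quantile of Beta(x + 1, n − x). For 4/20 at 90% this gives 7.1% to 40.1%. The distance from 20% down to the lower limit is 12.9 points, which matches the stated precision of 13%. The half-width is (40.1 − 7.1)/2 = 16.5 points, so the stated figure is the lower-side distance only. That does not affect the present point, but it confirms the base case and the method.

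**Step 1: how each rule classes the patients in dispute.**

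| Patient | SAP 6.4.1 formula, read literally | Table 14.2.1.1 footnote | Alive and progression-free |
|---|---|---|---|
| Dies before day 180, no documented progression | Success | Failure | Failure |
| Stops drug before day 180; alive and without progression at 6 months | Success | Failure | Success |

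The footnote fails the first patient because the last dosing day cannot fall after death, so treatment duration cannot reach 180 days, and the patient stays in N. It fails the second patient for the same mechanical reason, although that patient meets the endpoint as worded.

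**Step 2: size of the effect of deaths.** Start from 4 patients alive and progression-free at day 180 and add *d* deaths without documented progression.

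| d (assumed) | 6.4.1 literal: (4 + d)/20 | Exact 95% CI | Footnote rule: 4/20 | Exact 95% CI |
|---|---|---|---|---|
| 0 | 20% | 5.7 to 43.7 | 20% | 5.7 to 43.7 |
| 1 | 25% | 8.7 to 49.1 | 20% | 5.7 to 43.7 |
| 2 | 30% | 11.9 to 54.3 | 20% | 5.7 to 43.7 |
| 3 | 35% | 15.4 to 59.2 | 20% | 5.7 to 43.7 |

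The footnote column assumes that all 4 successes stayed on drug for 180 days.

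**Step 3: the opposite error.** If one of those 4 had stopped the drug before day 180 without progressing, the footnote rule would give 3/20 = 15%, while the alive-and-progression-free count stays at 4/20 = 20%. With one early death and one such early stopper, the literal formula gives 5/20 = 25% and the footnote gives 3/20 = 15%: 10 points apart on the same data, with neither equal to the 20% who are alive and progression-free.

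**Step 4: does the SAP settle which rule governs?** It does not. Table 14.2.1.4 is built on the format of Table 14.2.1.1. If the 180-day footnote carries over, nobody in the 6-month numerator can have died before day 180, and naming death in that row adds nothing. If the two labels are meant to differ, the footnote cannot be the primary rule.

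**The case against.** The strongest reply is that the primary shell already protects the result. Its footnote is the only operational counting rule in the SAP, and under it an early death adds 0 points. SAP 6.4.1 is silent on death; it does not say that a death is a success. The alive-and-progression-free rate has its own tables (14.2.1.4 to 14.2.1.6), Kaplan-Meier PFS counts death from any cause, and deaths have a safety table, so early deaths would be visible.

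Most of this stands, and it limits the point. A reader might infer that the plan as written will count early deaths as successes and so inflate the primary result. The documents do not support that, because the footnote points the other way. A reader might also infer a bias towards the more toxic dose. That would need more such deaths in one arm than in the other, and no figure in the documents shows this. The footnote to Table 14.1.1.1 mentions a death of unknown cause, but as a non-related event and without arm, day or progression status. Nor does Protocol 7.4.4 show that a death attributed to progression leaves no progression record: the withdrawal listing (16.2.1.4) has fields for progression date, death date and cause of death.

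The reply does not remove the conflict. The footnote rests on a criterion that is absent from the definition, and it misclassifies a different group of patients. Correcting it back to the wording of 6.4.1 would restore the problem with deaths.

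**Conclusion.** The primary variable is not uniquely defined. Under the formula in SAP 6.4.1, each death before day 180 without documented progression raises the result by 5 points in an arm of 20 (20% to 25% for one, 30% for two). Under the shell footnote it adds nothing, but each patient who stops the drug before day 180 without progressing is lost from the numerator, also at 5 points each. Neither rule gives the proportion alive and progression-free.

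The size rests on a base case of 4/20, taken from the sample-size assumption, and on assumed counts of such patients. If an arm has none of either kind, the two rules agree. The finding is a conflict between definition and shell that can change the primary result; it does not show that the result is inflated or that either dose is favoured.

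**What to change.** In SAP 6.4.1 and 8.7.1, define success as alive and without RECIST 1.1 progression at 6 months (day 180), with death from any cause before then a failure and all patients in the analysis set as denominator. Replace the treatment-duration footnote in Tables 14.2.1.1 to 14.2.1.3 with this rule, and align the 6-month row of Table 14.2.1.4 and the two tables derived from it. The same text should say how a patient is classed who stops the drug early and is alive but has no scan near day 180, because the schedule of events shows no imaging after the EOT visit. Declare the clarification in SAP 5.2, which now states that nothing has changed from the protocol analyses.

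The cost is a few sentences and one programming condition; death and progression dates are already planned for Listing 16.2.1.4. The percentage may be slightly less favourable than under the literal 6.4.1 formula, and could be higher than under the footnote if patients stopped early without progressing. The primary table will match the 6-month PFS row, so one can refer to the other. A progression-only count can stay as a labelled descriptive row if wanted.
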